- [17] Blood collection before administration of BNT112.
- [18] Blood collection 4 h (±30 min) after administration of BNT112.
- [19] Variable time point; either during screening ≤7 d or at C1D1 before administration of BNT112.
- [20] At 6 weeks ( $\pm 1$  week) after the surgery (radical prostatectomy).
- Only for Arm 2 (and at screening for all patients if the patient is not yet randomized), thyroid hormones (thyroid stimulating hormone [TSH], free thyroxine [fT4] and triiodothyronine [T3]) will be performed at the times listed and as clinically indicated at the investigator's discretion.
- On-treatment tumor samples from biopsies or tumor resections done as part of the clinical management of the patient (e.g., palliative surgery) will optionally be provided for additional potential biomarker research.
- [23] Randomization can be performed up to 1 day before C1D1.

CONFIDENTIAL Page 32 of 122

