# 8.3.3. Surgery-related Assessments

In this trial, newly diagnosed LPC patients randomized to Arms 2 and 3 will be given neoadjuvant treatment with BNT112 up to Cycle 8 (week 21) before surgery (radical prostatectomy).

The surgery is scheduled after the EoT visit and is not part of this trial. However, the following trial-related procedures/assessments are required and will be documented in the eCRF:

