# 10.3.3. Recording and Follow-Up of AE and/or SAE

### **AE and SAE Recording**

The investigator needs to assess and document any AE regardless of association with the use of the trial treatment during the period of observation (from signing ICF until FU-D30 for Part 1 and Part 2 Arm 1B and Arm 3, and FU-D90 visit for Part 2 Arm 1A, Arm 1B switch-over patients, and Arm 2).

- Data pertaining to AEs will be collected during each trial visit either. Based on the patient's spontaneous description or investigator's inquiry or discovered in the course of examinations done during the visit, clinical significance of any sign or symptom needs to be evaluated by the investigator.
- Clinically significant findings need to be documented as AEs in the source data and eCRF. Findings that are evaluated and documented in the source data as not clinically significant (e.g., an abnormal laboratory value without any clinical manifestation), should not be documented as AE.
- The investigator will then record all relevant AE information in the eCRF and perform an assessment on:
  - o Intensity according to CTCAE v5.0
  - Seriousness
  - Outcome
  - O Drug relationship of the AE to the trial treatment
  - o Any trial treatment action and/or any other action taken
- All assessments as well as AE term (diagnosis/description), start date and time of onset, end date and time need to be documented on the source data and eCRF.
- It is not acceptable for the investigator to send photocopies of the patient's medical records to the sponsor in lieu of completion of the AE eCRF page.
- There may be instances when copies of medical records for certain cases are requested by the sponsor. In this case, all patient identifiers, with the exception of the patient number, will be redacted on the copies of the medical records before submission to the sponsor.
- To avoid colloquial expressions, the AE should be reported in standard medical terminology. The investigator will attempt to establish a diagnosis of the event based on signs, symptoms, and/or other clinical information. Whenever possible, the diagnosis (not the individual signs/symptoms) will be documented as the AE. If a definitive diagnosis is not possible, the individual signs and symptoms should be recorded.

CONFIDENTIAL Page 99 of 122

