# Relationship to prostate cancer surgery

- For patients in Part 2 Arms 2 and 3 the investigator should also assess the relationship of the event to the prostate cancer surgery. These events have to be reported in the eCRF on Adverse Event pages as "related to prostate cancer surgery".
- The investigator will also consult the respective IB and/or Product Information, for marketed products, in his/her assessment.
- For each AE/SAE, the investigator must document in the medical notes that he/she has reviewed the AE/SAE and has provided an assessment of causality.
- There may be situations in which an SAE has occurred and the investigator has minimal information to include in the initial report to the sponsor. However, it is very important that the investigator always makes an assessment of causality for every event before the initial transmission of the SAE data to the sponsor.
- The investigator may change his/her opinion of causality in light of follow-up information and send a SAE follow-up report with the updated causality assessment.
- The causality assessment is one of the criteria used when determining regulatory reporting requirements.

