### **SAE Exemptions**

In general, SAEs are defined according to ICH Topic E2A (CPMP/ICH/377/95), EU Directive 2001/20/EC and ENTR/CT-3 (see Section 10.3.2). In the present trial, some events are excluded from the SAE definition. The following events do not need to be reported as SAEs:

- AEs and SAEs occurring later than 30 days (for Part 1 and Part 2 Arm 1B and Arm 3) and 90 days (for Part 2 Arm 1A, Arm 1B switch-over patients, and Arm 2) after the last administration of trial medication must only be reported by the investigator to the sponsor if a relationship to trial treatment or trial procedure is suspected.
- Hospitalizations for respite care will not be considered as reportable SAE.
- Hospitalizations solely for coordination of care, including hospice arrangements, will not be considered as reportable SAE.
- Hospitalizations that were necessary solely because of patient requirement for outpatient care outside of normal outpatient clinic operating hours will not be considered as reportable SAE.

CONFIDENTIAL Page 104 of 122

- Planned hospitalizations required by the protocol (e.g., for trial treatment administration or insertion of access device for trial treatment administration) will not be considered as reportable SAE.
- Hospitalizations for procedures or interventions of a pre-existing condition of the patient (elective surgery = planned, non-emergency surgical procedure) will not be considered as a reportable SAE (e.g., prostate cancer surgery planned for patients in Part 2 Arms 2 and 3)
  - o if it was planned and documented in patient record before the trial-specific patient informed consent was signed (ICF for trial participation, see Section 10.1.3, or
  - o if it was scheduled during the trial when elective surgery became necessary and the patient has not experienced an AE.

Nevertheless, this kind of hospitalization should be avoided during trial treatment.

- Hospitalization of a patient for monitoring and symptomatic treatment for up to 24 h due to a transient inflammatory reaction of Grade 1 or 2 will not be considered as a SAE (but needs to be documented as AE).

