8.9.3 Adverse events

AEs will be coded using the MedDRA® (version 22.1 or later version) coding system to get a SOC and PT for each AE and will be graded for severity using NCI CTCAE v5.0.

A **TEAE** is defined as any AE with an onset date on or after the first administration of IMP (if the AE was absent before the first administration of IMP (W_pro1 or cemiplimab, whichever comes first)) or worsened after the first administration of IMP (if the AE was present before the first administration of IMP).

AEs with an onset date more than 30 days (after the last administration of W_pro1) or 90 days (90 days after last administration of cemiplimab for Part 2, Arm 1A and Arm 2), respectively, after the last administration of W_pro1 or cemiplimab will be considered as treatment-emergent only if assessed as related to IMP by the investigator. TEAEs will be summarized overall and by treatment group for patients in the safety set.

For patients from Arm 1B who switch to cemiplimab monotherapy, the analysis of AEs will be additionally performed for each IMP separately, (i.e. only TEAEs from the first dose of W_pro1 until last dose of W_pro1 +30 days will be reported as TEAEs for Arm 1B).

In addition, **cemiplimab TEAEs** will be reported in separate AE tables using the subsequent cemiplimab monotherapy on progression set. Cemiplimab TEAEs are defined as TEAEs with an onset date on or after the first dose of cemiplimab until the last dose of cemiplimab +90 days. TEAEs with an onset within the 30 days after last dose of W_pro1 but after start of first cemiplimab treatment will be counted twice, as TEAE for Arm 1B and as cemiplimab TEAE in the respective tables and listings.

AEs started prior to first administration of IMP or AEs after last administration of IMP (follow-up AEs) will be included only in the AE listings.

AEs related to W_pro1

AEs related to W_pro1 are AEs with the item "Causality (relationship to W_pro1)" ticked "*Related*" in "*Adverse Events*" form of the eCRF. If the item is missing, the AE will be considered as related to W_pro1.

AEs related to cemiplimab

AEs related to cemiplimab are AEs with the item "Causality (relationship to cemiplimab)" ticked "*Related*" in "*Adverse Events*" form of the eCRF. If the item is missing, the AE will be considered as related to cemiplimab.

AEs related to IMP (W_pro1 + cemiplimab)

AEs related to IMP are AEs related to either W_pro1 or cemiplimab (or both).

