The number and percentage of patients for each category above will be summarized by SOC and PT as per MedDRA. If a SOC / PT is reported more than once for a patient, the patient will only be counted once for this SOC / PT. All AE summary tables will be sorted by descending frequency (%) by SOC and by PT within SOC with respect to the Parts 1 and 2 Total column. The number of events will be summarized in the same table.

The following AE tables by SOC and PT will be generated:

- TEAEs by System Organ Class and Preferred Term
- TEAEs related to IMP by System Organ Class and Preferred Term
- TEAEs related to W_pro1 by System Organ Class and Preferred Term

- TEAEs related to Cemiplimab by System Organ Class and Preferred Term
- Grade ≥ 3 (Maximum intensity) TEAEs by System Organ Class and Preferred Term
- Grade ≥ 3 TEAEs related to IMP by System Organ Class and Preferred Term
- Grade ≥ 3 TEAEs related to W_pro1 by System Organ Class and Preferred Term
- Grade ≥ 3 TEAEs related to Cemiplimab by System Organ Class and Preferred Term
- TEAEs related to trial procedure by System Organ Class and Preferred Term
- TEAEs related to prostate cancer surgery (Part 2 Arm 2 / Arm 3) by System Organ Class and Preferred Term
- Any Serious TEAEs by System Organ Class and Preferred Term
- Serious TEAEs related to IMP by System Organ Class and Preferred Term
- Serious TEAEs related to W_pro1 by System Organ Class and Preferred Term
- Serious TEAEs related to Cemiplimab by System Organ Class and Preferred Term
- Serious TEAEs leading to death by System Organ Class and Preferred Term
- Serious TEAEs leading to death related to IMP by System Organ Class and Preferred Term
- Serious TEAEs leading to death related to W_pro1 by System Organ Class and Preferred Term
- Serious TEAEs leading to death related to Cemiplimab by System Organ Class and Preferred Term
- TEAEs leading to IMP dose reduction by System Organ Class and Preferred Term
- TEAEs leading to W_pro1 dose reduction by System Organ Class and Preferred Term
- TEAEs leading to Cemiplimab dose reduction by System Organ Class and Preferred Term
- TEAEs leading to IMP dose delay by System Organ Class and Preferred Term
- TEAEs leading to W_pro1 dose delay by System Organ Class and Preferred Term
- TEAEs leading to Cemiplimab dose delay by System Organ Class and Preferred Term
- TEAEs leading to IMP dose modification by System Organ Class and Preferred Term

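### Adverse events related to prostatectomy are counted to 30 days after last dose in Arm 3 but to 90 days in Arm 2, so Table 14.3.1.11 has unequal ascertainment by arm

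*Protocol*

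**What the plan says.** **Collection window.** Protocol 10.3.3 (AE and SAE Recording) sets the AE observation period as "from signing ICF until FU-D30 for Part 1 and Part 2 Arm 1B and Arm 3, and FU-D90 visit for Part 2 Arm 1A". Arm 2 is in the same FU-D90 group. The schedule in Protocol 1.4 (double-asterisk footnote) counts FU-D30 from the last BNT112 dose. For Arm 2 it takes the later of 90 days after last cemiplimab and 30 days after last BNT112.

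**Surgery.** Protocol 8.3.3: "The surgery is scheduled after the EoT visit and is not part of this trial". EoT may fall up to 21 days after the last dose and may be combined with FU-D30 (Protocol 1.4). As far as the schedule can be read, its Surgery column has no AE entry.

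**Attribution.** For Arms 2 and 3, Protocol 10.3.3 says "the investigator should also assess the relationship of the event to the prostate cancer surgery".

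**After the window.** Under SAE Exemptions in the same section, later AEs and SAEs "must only be reported by the investigator to the sponsor if a relationship to trial treatment or trial procedure is suspected". Relationship to trial procedures and relationship to prostate cancer surgery are separate categories there.

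**Analysis.** SAP 8.9.3 applies the same split to treatment emergence: "AEs with an onset date more than 30 days (after the last administration of W_pro1) or 90 days" (the latter after cemiplimab, Arms 1A and 2) count only if related to IMP. It then lists "TEAEs related to prostate cancer surgery (Part 2 Arm 2 / Arm 3) by System Organ Class and Preferred Term", which becomes Table 14.3.1.11 on the safety set.

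**The concern.** The two windows are tied to the two drugs, which makes sense for drug toxicity. Surgical complications, however, follow the operation, and the operation comes at or near the end of the shorter window. A table of surgery-related events built on these windows therefore observes different stretches of the post-operative period in the two arms.

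Arms 2 and 3 are randomised 1:1, so readers will set the columns side by side. A surplus of surgical events in Arm 2 could then be read as an effect of cemiplimab when it reflects longer observation. The same AE data feed the pooled AE columns for monotherapy and combination therapy (SAP 8.1 and 13.4). Safety and tolerability is a primary objective in Part 2, and events that were never collected may not be recoverable later.

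**Working it through.** **Inputs.** Cycle length is 21 days and the last planned dose is C8D1 (Protocol 1.4). EoT is up to 21 days after last dose, or merged with FU-D30, here taken as day 30. The AE limit W is 30 days after last dose in Arm 3 and 90 in Arm 2 when both drugs stop together. The safety visit window is +7 days. Planned size is 20 patients per LPC arm (Protocol 9.2). The documents give no surgery day s, so it is varied.

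**1. The plan's own figure.** C8D1 is 7 × 21 = 147 days after C1D1, and 147/7 = 21.0 weeks. This agrees with the week 21 given in Protocol 8.3.3.

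**2. Days of AE capture left after EoT** = W − EoT day (in brackets, with the +7-day visit window):

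| EoT, days after last dose | Arm 3 | Arm 2 |
|---|---|---|
| 7 | 23 (30) | 83 (90) |
| 14 | 16 (23) | 76 (83) |
| 21 | 9 (16) | 69 (76) |
| 30 (merged with FU-D30) | 0 (7) | 60 (67) |

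The bracketed figures help collection only. The SAP rule for treatment emergence is a strict 30 days, so the extra 7 days do not reach Table 14.3.1.11.

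**3. Share of the first 30 post-operative days inside the limit** = max(0, min(30, W − s))/30:

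| Surgery, days after last dose | Arm 3 | Arm 2 |
|---|---|---|
| 7 | 23/30 = 77% | 100% |
| 14 | 16/30 = 53% | 100% |
| 22 | 8/30 = 27% | 100% |
| 28 | 2/30 = 7% | 100% |
| 30 to 60 | 0% | 100% |

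**4. Effect on the table (illustration).** Assume the same true 30-day risk p in both arms, uniform onset and 20 operated patients per arm. Expected patients shown = 20 × p × share.

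| p | Arm 2 | Arm 3, s = 14 | s = 22 | s = 28 | s ≥ 30 |
|---|---|---|---|---|---|
| 20% | 4.0 | 2.1 | 1.1 | 0.3 | 0 |
| 40% | 8.0 | 4.3 | 2.1 | 0.5 | 0 |
| 60% | 12.0 | 6.4 | 3.2 | 0.8 | 0 |

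The Arm 2 column holds for s up to 60. The risks are assumptions; the documents give none.

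**5. If cemiplimab stops first.** With the last cemiplimab dose d days before the last BNT112 dose, the Arm 2 limit is max(90 − d, 30) days after last BNT112. That is 69 for d = 21, 48 for d = 42 and 30 for d ≥ 60. The gap to Arm 3 shrinks and then disappears.

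**6. Routes for a late event in Arm 3 (after day 30).** If the investigator thinks the drug may be involved, the event is reportable and treatment-emergent, because the causality table in Protocol 10.3.3 classes possible as related. If the investigator judges it purely surgical, it is neither related to trial treatment nor, since surgery has its own category and lies outside the trial, to a trial procedure. It then has no required route.

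**The case against.** A reader might infer that surgical events in Arm 3 can hardly be captured at all, so that its column is near zero by construction. The documents do not support that. No section fixes the interval from last dose to surgery, EoT is only bounded by 21 days, and Protocol 7.1 lets the investigator bring surgery forward. With surgery on day 7, Arm 3 still covers 77% of the first 30 post-operative days; zero arises only from day 30 on. Bringing surgery forward does not by itself equalise the arms, however, because both limits still run from last dose.

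Nor do all late events escape. Possibly drug-related ones stay reportable and treatment-emergent, and Protocol 8.4.1 requires notification at any time of SAEs reasonably related to trial treatment or trial participation. The gap is confined to late events judged purely surgical.

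No formal comparison between arms is planned (SAP 4), the LPC setting is exploratory, and each arm has about 20 patients. This lowers the stakes, but safety in this trial is read from descriptive tables, and unequal windows mislead without a p-value.

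The content of the table is itself uncertain. SAP 8.9.3 also says that follow-up AEs after last IMP go only to listings. Taken literally, this would remove post-treatment surgical events from both arms, and it conflicts with the 30/90-day definition beside it. The trial-duration text in SAP 3.2 can be read as counting 30 and 90 days from EoT, which is longer but still unequal.

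**Conclusion.** The concern holds in a limited form. After a full course with EoT on day 21, post-EoT AE capture is at most 9 days in Arm 3 against 69 in Arm 2, and 0 against 60 if EoT is merged with FU-D30. Under the 30/90-day definition of treatment emergence, equal true surgical complication rates would show as an excess in Arm 2. The size of that excess cannot be stated, because it depends on a surgery date that the documents leave open and on whether both drugs stop together.

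Severity is moderate. The defect is certain in direction and cheap to remove, but confined to one descriptive table and its pooled columns. It does not touch ORR, the DLT assessment or the two-stage design.

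**What to change.** 1. **Protocol.** In both LPC arms, record AEs judged related to the prostatectomy through the 6-week (±1 week) post-surgery PSA timepoint in Protocol 1.4, footnote 20.
2. **SAP.** Define Table 14.3.1.11 as surgery-related AEs with onset from surgery to 6 weeks after it, among operated patients, regardless of the 30/90-day IMP window. Both arms are then observed for the same 42 days whatever the surgery date.
3. **Reconcile** this definition with the SAP 8.9.3 sentence that sends follow-up AEs only to listings.
4. **Patients already past that timepoint.** Also show both arms over a common window of 30 days after last dose, and state that it captures few post-operative days (at most 9 with EoT on day 21).

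**Cost.** A short amendment and one SAP paragraph. Footnote 20 is at present only a PSA sample, so an AE enquiry has to be added to it. Recording lengthens mainly in Arm 3: with surgery on day 22 the timepoint is day 22 + 42 = 64, which is 34 days beyond the present limit. In Arm 2 it lengthens only if surgery falls after day 90 − 42 = 48. The drug-related 30- and 90-day rules stay as they are.

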# **Assessment of Intensity**

The intensity of an AE (i.e., severity of organ toxicity) will be graded according to the NCI CTCAE v5.0. AEs that are not listed in CTCAE v5.0 should be classified according to the investigator's discretion as close as possible to CTCAE v5.0, based on the comparison with the most severe case encountered in past training and clinical experience.

The investigator will make an assessment of intensity for each AE and SAE reported during the trial and assign it to one of the following categories:

- Grade 1 Mild: Asymptomatic or mild symptoms; clinical or diagnostic observations only; intervention not indicated. An event that is easily tolerated by the patient, causing minimal discomfort and not interfering with everyday activities.
- Grade 2 Moderate: Minimal, local or non-invasive intervention indicated; limiting ageappropriate instrumental activities of daily living (ADL)\*. An event that causes sufficient discomfort and interferes with normal everyday activities.
- Grade 3 Severe: Severe or medically significant but not immediately life-threatening; hospitalization or prolongation of hospitalization indicated; disabling; limiting of self-care ADL\*\*. An event that prevents normal everyday activities. An AE that is assessed as severe should not be confused with a SAE. Severe is a category utilized for rating the intensity of an event; and both AEs and SAEs can be assessed as severe.
- Grade 4 Life-threatening consequences; urgent intervention indicated
- Grade 5 Death related to AE

\*\* Self-care ADL refer to bathing, dressing, and undressing, feeding self, using the toilet, taking medications, and not bedridden.

With regards the intensity of an AE the following needs to be documented in source data and eCRF:

- Initial intensity of the AE
- Maximum intensity of the AE
- For each change of intensity:
  - o New grade of intensity
  - Date of change (= start of new grade of intensity)
  - o Time of change (only if relevant)

A change of intensity only needs to be documented if there is a clearly definable change in grading of the AE (e.g., a laboratory result changes from severe to moderate according to CTCAE criteria).

An event is defined as "serious" when it meets at least one of the predefined seriousness criteria as described in the definition of an SAE, NOT when it is rated as severe.

CONFIDENTIAL Page 100 of 122

\* Instrumental ADL refer to preparing meals, shopping for groceries or clothes, using the telephone, managing money etc.

# Actions taken by the investigator

Actions taken by the investigator as a result of an AE have to be documented.

Action(s) taken with trial treatment (IMPs) by the investigator:

- Dose not changed (= continuation of trial treatment administration according to the trial protocol)
- Dose reduced (= reduction of the trial treatment dosage \*)
- Trial treatment withdrawn temporarily (= interruption and resumption); i.e.:
  - o Delayed administration of IMP within one vaccination cycle
  - o Delayed start of the next vaccination cycle
  - o Cancellation of administration at a given visit
  - o Interruption of IMP administration during a given visit
- Trial treatment permanently withdrawn (= discontinuation)
- Unknown (e.g., in case the patient is lost to follow-up)
- Not applicable (e.g., in case treatment with trial treatment has not yet started or event starts after last trial treatment administration)

\*If an increase of trial treatment dosage is intended according to the trial protocol and the dosage is kept in comparison to last administration of trial treatment, it needs to be documented as "Dose reduced."

Other action(s) that may be taken by the investigator include:

- None
- Initiation of a concomitant therapy for the treatment of the AE
- Termination of a concomitant treatment (please specify; e.g., if this might be the cause of the AE)
- Change of the dose of a concomitant treatment
- Hospitalization or prolongation of hospitalization (please complete SAE-Form)
- Initiation/termination of a non-drug therapy
- Other (please specify)

